## 1. GLOSSARY OF ABBREVIATIONS & TERMS

Abbreviation	Description (using lay language)
CARSK	Canadian-Australasian randomised trial of screening kidney transplant candidates for coronary artery disease
CAD	Coronary artery disease
MACE	Major adverse cardiac event
ESKD	End-stage kidney disease
ANZDATA	Australian and New Zealand
QoL	Quality of life
PTCA	Percutaneous transluminal coronary angiography
CABG	Coronary artery bypass grafting
CK-MB	Creatinine kinase
SBP	Systolic blood pressure
BARC	Bleeding Academic Research Consortium
eCRF	Electronic case report forms
QALY	Quality adjusted life years
KMSA	Kaplan Meier sample average
IPW	Inverse Probability Weighting
MBS	Medicare benefit schedule
PBS	Pharmaceutical benefits scheme
AR-DRG	Australian-refined Diagnosis related groups
KDQOL-36	Kidney disease quality of life instrument
EQ5D-5L	EuroQol – 5 Dimensions – 5 Levels
REDCap	Research electronic data capture
SLHD	Sydney local health district

### **3. FUNDING AND RESOURCES**

#### **3.1 SOURCE/S OF FUNDING**

Australia	National Health Medical Research Council Funded Clinical Trial Project Grant #1084454
New Zealand	New Zealand Heart Foundation
Canada	Canadian Institutes of Health Research

### **4. STUDY SYNOPSIS**

#### **4.1 BACKGROUND AND RATIONALE**

Cardiovascular disease is the most common cause of death while on the kidney transplant waiting list and after transplantation. Current standard care involves screening for coronary artery disease prior to waitlist entry, then every 1-2 years, according to perceived risk, until transplanted. The aim of screening is two-fold. Firstly to identify patients with asymptomatic coronary disease to enable either correction, by bypass surgery or angioplasty, or removal of the patient from the list, with the ultimate aim of preventing premature cardiovascular mortality at the time of, or soon after kidney transplantation. Secondly, from a societal perspective, to prevent mis-direction of scarce donor organs into recipients who experience early mortality. This current screening strategy is not evidence based, has substantial known and potential harms, and is very costly. Two major issues of uncertainty require addressing in sequence: (1) whether to periodically screen asymptomatic wait-listed patients for occult coronary artery disease; and (2) whether to revascularise coronary stenoses in asymptomatic patients prior to transplantation. The CARSK study seeks to address the first of these 2 issues.

#### **4.2 STUDY DESIGN**

CARSK is a multicentre, non-inferiority, 2-parallel-arm randomised trial.

#### **4.3 STUDY OBJECTIVES**

CARSK aims to

1. Test the hypothesis that after screening for wait list entry, no further screening for coronary artery disease (CAD) is non-inferior to the current standard care which is screening all asymptomatic wait-listed patients for CAD at regular intervals.
2. Compare the benefits and costs of not screening versus regular CAD screening from a health system perspective.

#### **4.4 TRIAL INTERVENTIONS**

People randomised to the intervention arm will receive no regular cardiac screening in the absence of symptoms of Coronary Artery Disease.

People randomised to the control arm will receive routine coronary artery disease screening. Additionally all trial participants who develop symptoms or signs of cardiac disease will be investigated and treated as per local protocol.

#### 4.5 STUDY POPULATION

We plan to enrol a total of 3,306 patients for the whole trial, 1100 people on the kidney transplant waiting list in Australasia and 2206 in Canada.

#### 4.6 STUDY ENDPOINTS

*Primary efficacy endpoint:* major adverse cardiac event (MACE), defined as any of the following: cardiovascular death, myocardial infarction, emergency revascularisation, hospitalisation with unstable angina.

*Primary safety endpoint:* the above MACE endpoint plus complications from cardiac diagnosis or treatment including major bleeding requiring transfusions or hospitalizations, vascular intervention subsequent to cardiac interventions stroke and all-cause death.

*Secondary endpoints:* death, cardiovascular death, procedure-related death, myocardial infarction, emergency revascularisation, stroke, hospitalisation with unstable angina, hospitalisation with heart failure, hospitalisation with arrhythmia, major bleeding, health-related quality of life (QoL), time off list (including number of temporary suspension and duration of each suspension), cost-effectiveness, incidence of permanent removal from list for cardiac causes; incidence of transplantation and cancellation of transplant due to CAD.

#### 4.7 STUDY ANALYSES

Cox models will be used to assess the time to first MACE event and death. Competing risk models will be used to assess the time to all other outcomes, adjusting for death as the competing risk.

## 5. INTRODUCTION/BACKGROUND INFORMATION

### 5.1 LAY SUMMARY

The CARSK trial will enrol people who are already on the kidney transplant waiting list, and who don't have any symptoms of new heart problems. The patients enrolled will stay in the study for a maximum of 4 years in Australia and New Zealand and 5 years in Canada. While they are in the study, people will be followed up as usual – they will not have to have any extra appointments but will receive a 6-monthly phone call to check wait-list status and exclude any CAD events. They will also be asked to complete cost and quality of life questionnaires. The trial will use chance to allocate people to either getting no regular heart testing while they wait for a kidney transplant, or to get regular (every year or every second year) heart testing. We will make sure everyone gets tested if they develop any symptoms of heart problems. The trial will measure what happens to people, and particularly whether they develop any heart problems, whether they get a kidney transplant, and whether they have any heart problems after a transplant. The study is important as we know the most common cause of death for people on dialysis or after a transplant is heart related. We don't know if finding heart disease and trying to treat it early, before it is bothering people, is a good idea – even though this is what is done at the moment. We think testing and treating people who don't have symptoms might cause more problems than it solves - it might remove them from the waiting list unnecessarily, or put them through tests and procedures or operations that they don't really need, and waste a lot of peoples' time and money without good reason. This CARSK study will help us work out whether regular testing is helpful, by showing us whether there is any difference to what happens to people if they are tested or not. The study investigators think it is likely that there will be no difference, so we have used best scientific principles to design the CARSK study to test whether we are right.

### 5.2 BACKGROUND INFORMATION

Kidney transplantation prolongs survival, improves quality of life, and is less costly than dialysis for people with end-stage kidney disease (ESKD).(1, 2)There are over 12,000 Australians, 2,600 New Zealanders and 20,000 Canadians who currently depend on dialysis for survival (3, 4). As quality of life and life expectancy are substantially improved by transplantation, the majority of these patients would like to receive a transplant. However, as only 800-1000 kidney transplants are performed annually, demand for transplantation far exceeds supply. Patients routinely wait on dialysis for an average of 2 to 7 years before they receive a deceased donor kidney transplant.(5, 6) The waiting list is dynamic, with new people joining, some being transplant, and others being removed temporarily or permanently.

Wait-listed patients are at high risk for coronary artery disease (CAD) compared to the general population but are commonly asymptomatic. Exposure to dialysis is a major factor increasing the risk of cardiac events before and after transplantation.(7) Due to prolonged waiting times for a deceased donor kidney, the cardiac fitness of wait-listed patients must be maintained for long time periods. The risk of cardiac events and death in wait-listed patients is bi-modally distributed, being high

whilst on dialysis, a transient increase immediately following transplantation in association with surgical stresses and high dose immunosuppression, then substantially reduced to a lower baseline after successful transplantation. (8, 9) The cumulative incidence of myocardial infarction ranges from 8.7% to 16.7% by 3 years after wait-listing, and from 4.7% to 11.1% after 3 years of kidney transplantation.(10, 11) Cardiovascular disease is the most common cause of death in both wait-listed patients and patients with a functioning transplant, accounting for 30% of mortality overall.(12) CAD is difficult to diagnose in ESKD patients who may not develop the classic symptoms of angina because of uremia, physical limitations, diabetes, neuropathies and other factors. For example, among patients hospitalized with myocardial infarction, chest pain at presentation was less common in dialysis (44%) compared to non-dialysis patients (68%).(13)

The average age and medical complexity of wait-listed patients is increasing. The proportion of transplant candidates 50 years and above increased by 62% between 1991 and 2011,(12) while the percentage with diabetes increased from 23% to 28% between 1998 and 2008.(14) Approximately 15% of waitlisted patients, and 19% of those living with a functioning transplant are over 65 years.(6) Increasing age and co-morbidity substantially increases the risk of CAD. Changing donor characteristics are also likely to increase CAD risk after transplantation. In a bid to expand the donor pool and address the organ shortage, kidneys from 'extended criteria' donors (particularly older people with medical illnesses), are increasing in number (22% total donors in 2012). Recipients of these kidneys have more peri-operative complications, and a higher risk of peri-operative cardiac events, likely due to the higher incidence of delayed graft function (requirement for dialysis after transplantation) and related complications. The average donor age has increased by approximately 0.5 years per annum for the past 10 years and was 49.7 years in 2012 – the highest on record. (15)

Current CAD screening practice is not evidence based. Current transplant clinical practice guidelines recommend two phases of screening for CAD i) *prior* to acceptance onto the waiting list, *and* ii) screening at regular intervals (every 1-2 years) *after* wait-listing.(16) The aim of screening is to identify CAD by non-invasive tests (i.e. Exercise Stress test, Myocardial Perfusion Scintigraphy or Dobutamine Stress Echo or similar). Patients with abnormal non-invasive tests are typically removed from the waiting list and undergo coronary angiography followed by revascularization of any hemodynamically critical stenosis by coronary angioplasty with or without coronary stenting, or coronary artery bypass grafting. (16) Once the procedure is deemed successful and the patient recovered, they may be returned to the active transplant waiting list. Those with advanced, unmodifiable CAD are unlikely to have a survival benefit from transplantation and so are not listed, or if already on the list, are delisted. This strategy aims to promote survival peri-operatively and in the short-medium term after transplantation. From a societal perspective, it is also imperative to prevent mortality in the early post-transplant period as this also results in the loss of a donated kidney, which incurs an opportunity cost for those who remain on the waitinglist.

Although regular, non-invasive cardiac screening is the current standard of care, only 1 randomized single centre trial performed in 1992 has ever been performed to evaluate this strategy. (17) This study recruited 26 insulin dependent diabetic transplant candidates with coronary artery stenoses greater than 75%, atypical or no chest pain, and a left ventricular ejection fraction greater than 35%, and randomised them to medical therapy (calcium channel blocker plus aspirin) or revascularization

with angioplasty or coronary artery bypass grafting (CABG). Among the 13 patients assigned to medical therapy, 10 incurred a cardiac end point (including 4 deaths) compared to 2/13 revascularised patients ( $p < 0.01$ ). The study was prematurely terminated because of the imbalance of events between groups and slow recruitment. The applicability of this study is limited for several reasons: i) medical therapy has improved substantially ii) the study focused on a specific high-risk population (type 1 diabetics) who now represent <10% of the wait-listed population; iii) the study evaluated one time screening in an era when transplant waiting times were dramatically shorter; iv) the trial had few events overall hence the results have substantial fragility, and the trial was stopped early for a “too good to be true” treatment effect.

The rationale for screening is challenged by observations that not all the excess cardiovascular disease burden of ESKD is related to CAD. ESKD patients most frequently die of sudden cardiac death, that may be arrhythmogenic in origin or may be related to uremic cardiomyopathy, and not atherosomatous disease. The rationale for screening for critical coronary stenoses also ignores evidence that the usual mechanism of myocardial infarction is atherosclerotic plaque rupture followed by thrombosis and occlusion of the affected coronary artery. The risk of plaque rupture in the peri-operative period is related to tachycardia, increased sheer stress, and a hypercoagulable state. The most occlusive plaques are not necessarily prone to rupture and thrombosis. One third of patients with peri-operative myocardial infarction sustain damage in areas distal to noncritical stenoses. Finally, the available screening tests do not necessarily identify plaques at risk of rupture and thrombosis.

**Does routine screening have other downsides?** Screening may paradoxically increase morbidity and mortality by: i) exposing patients to risk of angiography and revascularization procedures; or ii) by delaying or excluding patients from lifesaving kidney transplantation because of their perceived CAD status. In other settings, for example in most surgical candidates, screening is not beneficial. However, the goals of screening transplant candidates differ somewhat from other settings, and include not only prevention of peri-operative cardiac events, but also maintenance of transplant eligibility during wait-listing, and long-term post-transplant survival. The current standard of care may be harmful. The potential harmful outcomes related to the current strategy of screening and revascularization of asymptomatic transplant candidates are summarized in Table 1 below.

A recent joint Scientific Statement from the American Heart Association and the American College of Cardiology Foundation concluded “that there is no strong evidence for or against routine cardiac screening of asymptomatic transplant candidates” and that more evidence from randomized clinical trials was needed. The lack of evidence in the transplant setting has led to confusion about the optimal management of transplant candidates: the two major issues of uncertainty are whether to screen asymptomatic patients for occult CAD, and whether to revascularise coronary stenoses in asymptomatic, screen-detected patients.

**Table 1: Evidence of increased harm from CAD screening in ESKD**

Complications of revascularization are higher in people with ESKD				
Population	Event Type	Event Rate	citation	
U.S. Dialysis patients 1978-95	2year mortality post PTCA	52%	(23)	
	2year mortality post CABG	44%	(23)	
U.S. Transplant recipient 1995-99	2year mortality post PTCA	18%	(24)	
	2year mortality post CABG	17-26%	(24)	
Non-ESKD patients reported by Bari Investigators	5 year mortality post PTCA	14%	(25)	
	5 year mortality post CABG	12%	(25)	
2	Asymptomatic ESKD patients may be considered too high risk for surgery and excluded from transplantation rather than revascularized		(26)	
3	Screening prolongs waiting time prior to transplantation: Audit of 130 wait-list candidates in Canada found 45 were put on hold for transplantation because of abnormal screening tests for a mean of 446 days (only 5/45 were ever revascularized).			Audit for grant
4	Relative increased bleeding risk with use of anti-coagulation after revascularization in ESKD patients and most surgeons will not transplant anti-coagulated patients. In particular, clopidogrel is commonly prescribed for 6 months after coronary stent placement, but is a relative contraindication to transplant surgery.		(27)	
5	Angiography causes loss of residual kidney function. Preservation of residual kidney function is associated with increased dialysis survival		(28)	

PTCA= percutaneous coronary angiography, CABG= coronary artery bypass grafting

**Data to justify the focus on CAD screening tests only after people are wait listed** The CARSK trial will focus on the use of screening tests *after* activation to the waiting list because *Physicians are unwilling to forgo initial cardiac evaluation* because these tests are considered essential to determine initial transplant eligibility. This assumption was proven by surveying current Canadian transplant centres: of 15 adult Transplant Centres, all centres screen for CAD during the initial transplant evaluation. Most (13/15) did not support randomization of patients to use or non-use of cardiac investigations during the initial evaluation of patients for activation onto the waiting list. *In contrast, there is clinical equipoise around the use of screening tests for CAD after wait-listing:* All centres reported screening for CAD after wait-listing. The majority of transplant centres (11/15) had a screening protocol, while in 4/15 centres transplant physicians individually selected patients for screening. The frequency of screening reported in hypothetical patient scenarios equalled or exceeded that recommended in current transplant guidelines.(18) All 15 centres were willing to randomize patients to regular or selective screening after wait-listing. The largest health services burden is related to screening practices after wait-listing (typically 2-7 years), rather than the one time testing prior to placement on the waiting list.

**Data to demonstrate screening for CAD is expensive.** Our Canadian investigators studied costs in a pilot study and found, of 604 wait-listed patients in British Columbia followed for  $3.7 \pm 1.8$  years, 530 non-invasive cardiac screening tests with an estimated cost of over C\$530,000 were required by current guidelines.(18) When the additional costs of program administration, coronary angiography, consultations and revascularization procedures in patients with abnormal screening tests were considered, the current non-evidence based strategy costs a minimum of \$15 million per year in Canada.(25) The estimated cost of a single screening test for those wait listed in Australia is in excess of \$1.1 million each year, and for the over 90,000 wait-listed patients in the United States is \$210 million.(26, 27) To date no studies have examined the cost-effectiveness of screening strategies for

coronary artery disease. In order to ensure health care system sustainability and maximize patient outcomes given finite health care resources, it is critical that the effectiveness and cost-effectiveness of screening strategies be determined.

**Data to suggest selective screening may be safe in wait listed patients:** The 604 wait listed Canadians in the above pilot study only underwent screening based on on-going clinical evaluation.(18) This strategy resulted in fewer screening tests than recommended by guidelines (n =171 versus 530 tests), and no difference in cardiovascular events (cardiovascular event rate in patients without the recommended frequency of cardiac tests was 6.7 [95% CI, 5.2 to 8.7] per 100 patient-years, and in those screened regularly was 9.9 [95% CI, 7.1 to 13.7].(18) Two other observational studies also suggest that selective screening may be safe: in a single centre study of 514 wait-listed candidates who were screened based on clinical judgment of the treating physician, the incidence of cardiac events at 5 years in the 224 patient who were not screened was 5.3% compared to 19.7% among the 290 patients who were screened. (28) Similarly, in another study of 600 wait-listed patients, 174 patients were considered high risk based on clinical criteria and underwent screening for CAD and only 5 (2.9%) were revascularised. Cardiac events were higher in screened patients 12/174 (6.9%) versus unscreened patients 19/426 (4.5%).(29) Selection bias is likely in all these studies: only an RCT can answer the question definitively. The first phase will confirm protocol adherence, patient enrolment and consent rates of the 144 wait-listed participants who will be randomised to no screening versus routine screening for CAD, aiming to produce a 95% confidence interval equal to the sample adherence prevalence plus or minus 5% when the true prevalence of adherent patients is hypothesized to be 90%.

## 6. STUDY OBJECTIVES

### 6.1 RESEARCH QUESTION

Using randomised controlled trial design, with participants wait listed for kidney transplantation we will

- test the hypothesis that not screening asymptomatic wait-listed kidney transplant candidates for coronary artery disease is non-inferior to serial screening at regular interval (i.e. annually) using non-invasive cardiac screening tests (i.e. myocardial perfusion scintigraphy or dobutamine stress echo) for the composite primary efficacy outcome of major adverse cardiac event (MACE) defined as cardiac death, non-fatal myocardial infarction, urgent coronary revascularization and hospitalization for unstable angina.
- compare the benefits and costs of screening and subsequent treatment at wait list entry versus regular CAD screening from a health system perspective.

### 6.2 OUTCOME MEASURES

*Primary efficacy endpoint:* major adverse cardiac event (MACE), defined as any of the following: cardiovascular death, myocardial infarction, emergency revascularisation, hospitalisation for unstable angina.

*Primary safety endpoint:* the above MACE endpoint plus complications from cardiac diagnosis or treatment including major bleeding requiring transfusions or hospitalizations, vascular intervention subsequent to cardiac interventions stroke and all-cause death.

*Secondary endpoints:* death, cardiovascular death, procedure-related death, myocardial infarction, emergency revascularisation, stroke, hospitalisation with unstable angina, hospitalisation with heart failure, hospitalisation with arrhythmia, major bleeding, health-related quality of life (QoL), time off list (including number of temporary suspension and duration of each suspension), cost-effectiveness, incidence of permanent removal from list for cardiac causes; incidence of transplantation and cancellation of transplant due to CAD.

**Table 2: Outcome definitions**

Outcome	Definition (31-32)
Cardiovascular death	Cardiovascular death is defined as any death with a cardiovascular cause and includes those deaths after a cardiovascular procedure (eg, percutaneous coronary intervention), cardiac arrest, myocardial infarction, pulmonary embolus, stroke, and haemorrhage or deaths due to an unknown cause. Non cardiovascular death is defined as any death owing to a clearly documented non cardiovascular cause (eg, trauma, infection, malignancy).
Myocardial infarction	Myocardial Infarction (MI) is defined as the presence of any 1 of the

[figure not shown]
	
following 3 criteria:
 
 
1. A typical rise of troponin or a typical fall of an elevated troponin detected at its peak post-surgery in a patient without a documented alternative explanation for an elevated troponin (e.g. pulmonary embolus) OR a rapid rise and fall of CK-MB. This criterion also requires that 1 of the following must also exist:           
 
a. Ischemic signs or symptoms (i.e., chest, arm, neck, or jaw discomfort; shortness of breath, pulmonary edema)
 
b. Development of pathologic Q waves present in any two contiguous leads that are <math>\geq</math> 30 milliseconds
 
c. ECG changes indicative of ischemia (i.e. ST segment elevation [<math>\geq</math> 2mm in leads V1, V2, or V3 OR <math>\geq</math> 1mm in other leads], ST segment depression [<math>\geq</math> 1mm], or symmetric inversion of T waves <math>\geq</math> 1mm) in at least two contiguous leads
 
d. Coronary artery intervention (i.e., PCI or CABG surgery)
 
e. New or presumed new cardiac wall motion abnormality on echocardiography or new or presumed new fixed defect on radionuclide imaging
 
 
 
2. Pathological findings of an acute or healing myocardial infarction
 
3. Development of new pathological Q waves on an ECG if troponin levels were not obtained or were obtained at times that could have missed the clinical event
 

Emergency revascularisation	Emergency revascularisation within 1 month of presentation of new or progressive symptoms of coronary artery disease
Hospitalisation with unstable angina	Pain or equivalent with the presence of dynamic ECG changes, that requires hospitalisation. This classification require that 4 separate criteria be met: a) Worsening ischaemic discomfort b) Unscheduled hospitalization c) Objective evidence of myocardial ischaemia and d) Negative cardiac biomarkers
Hospitalization	Hospitalisation is defined as an admission to an inpatient unit or a visit to an emergency department that results in at least a 24-hr stay.
Stroke	A new focal neurologic deficit thought to be vascular in origin with signs and symptoms lasting $>24$ hours or leading to death
Procedure Related Death	Death caused by the immediate complication(s) of a Cardiovascular procedure
Major bleeding	
Bleeding Academic Research Consortium (BARC) type 3 and 5.
 
Type 3a: Overt bleeding plus hemoglobin drop of 3 to <math><5</math> g/dL* (provided hemoglobin drop is related to bleed). Any transfusion with overt bleeding
 
Type 3b: Overt bleeding plus hemoglobin drop <math><5</math> g/dL* (provided hemoglobin drop is related to bleed). Cardiac tamponade. Bleeding requiring surgical intervention for control (excluding dental/nasal/skin/hemorrhoid). Bleeding requiring intravenous vasoactive agents.
 
Type 3c: Intracranial hemorrhage (does not include microbleeds or hemorrhagic transformation, does include intraspinal) Subcategories confirmed by autopsy or imaging or lumbar puncture. Intraocular bleed compromising vision
 
Type 5: fatal bleeding

	Type 5a: Probable fatal bleeding; no autopsy or imaging confirmation but clinically suspicious
	Type 5b: Definite fatal bleeding; overt bleeding or autopsy or imaging confirmation

Definitions adapted from: 2014 ACC/AHA Key data elements and definitions for cardiovascular endpoint events in clinical trials,(30) Rational, design and organization of Perioperative Ischaemic Evaluation (POISE) trial: A randomized controlled trial of metoprolol versus placebo in patients undergoing noncardiac surgery,(31) and Standardised Bleeding Definitions for Cardiovascular Clinical Trials.(32)

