### **10.2 POWER CALCULATIONS**

We conservatively estimate an average MACE rate of 6%: MACE rates in the U.S. range from 8.7 % in the first year after a kidney transplant to 13.2 % per year on the waiting list.(41) Unpublished data in Australia and Canada show lower rates of 3% and 8% respectively. The lowest MACE rate would be observed if *all* patients underwent transplantation rapidly (i.e. one year wait-listing (MACE 8%), followed by one year of post transplant follow up (MACE 3%)). In this hypothetical scenario, the

[figure not shown]
average MACE rate would be 5.5%. We estimate that 50% of participants will receive a kidney transplant during the study - therefore the majority of patient follow up time will be accrued on the waiting list (when the MACE rate is high) rather than after a KTX justifying our estimated average MACE rate of 6%.

Using a MACE rate of 6% per year and non-inferiority defined as a Hazard Ratio (HR) of MACE  $< 1.25$ , randomization of **3306 patients** will give us 80% power using a two-sided 5% significance level to claim no screening is non-inferior to regular screening if the absolute difference in MACE in the no screening group is  $< 1.4\%$  higher (i.e. 7.4% versus 6.0 %) than in the regular screening group (Fig 2). This is lower than the 2% absolute increase in MACE Canadian transplant physicians indicated would be unacceptable in a survey prior to our pilot trial.

Enrolment of 3306 patients requires recruitment of  $\leq 4$  patients per month per centre. This rate is feasible, and was achieved in our pilot trial. Figure 2 shows the study power for MACE rates between 5 -13% per year. These calculations take into account the different study follow-up in Canada (5 years) and Australasia (4 years), and allow for a 10% drop-out rate.

Power calculations were performed using the **Non-inferiority Logrank Tests** in PASS 12 (NCSS, LLC. Kaysville, Utah, USA. [www.ncss.com](http://www.ncss.com)).

Figure 2: Study power for MACE rates

- For all power calculations, non-inferiority is defined as an absolute increase in the Hazard Ratio (HR) of MACE  $< 1.25$ , Two-sided alpha is 5%, and the total sample size is fixed at N=3306

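### Table 2 accepts a falling troponin as MI only when its peak is post-surgical, so some surviving wait-listed patients first sampled at or after the peak cannot be counted as MI

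*Protocol*

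**What the plan says.** Section 6.2 defines the primary MACE as any of "cardiovascular death, myocardial infarction, emergency revascularisation, hospitalisation for unstable angina". The primary safety endpoint includes MACE, and MI is also a secondary endpoint in its own right.

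Table 2 allows MI by any one of three criteria:

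- **Criterion 1** needs a biomarker pattern plus one supporting feature (a to e). The pattern is "A typical rise of troponin or a typical fall of an elevated troponin detected at its peak post-surgery", with an exclusion for a documented alternative cause of the troponin elevation, "OR a rapid rise and fall of CK-MB". Surgery is not defined and no time window is attached to it.
- **Criterion 2** is "Pathological findings of an acute or healing myocardial infarction".
- **Criterion 3** is "Development of new pathological Q waves on an ECG if troponin levels were not obtained or were obtained at times that could have missed" the event.

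The note under Table 2 lists among its sources the "Rational, design and organization of Perioperative Ischaemic Evaluation (POISE) trial", a trial in noncardiac surgery. Section 10.2 expects half of the participants to be transplanted during the study and concludes that "the majority of patient follow up time will be accrued on the waiting list".

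**The concern.** The surgical condition suits a trial in which every participant has an operation. Here most time at risk is on the waiting list, without one. The troponin part of criterion 1 therefore treats the same biochemical pattern differently according to whether the patient has had surgery.

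Two things are at stake. The first is lost events: MI is a component of the primary endpoint, and power in a time-to-event comparison depends on the number of events. The second is comparability: the protocol itself expects screening to delay or exclude some patients from transplantation (section 5.2) and lists incidence of transplantation as a secondary endpoint. A definition that is easier to meet after surgery ties endpoint capture to something that allocation may alter.

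Late or atypical presentation is credible in this population. Section 5.2 says coronary disease is hard to diagnose in end-stage kidney disease, and that chest pain at presentation with MI was less common in dialysis patients (44%) than in others (68%). That does not measure how often the first sample comes after the peak.

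**Working it through.** **Step 1: trace every route.** Take a wait-listed patient with ischaemic symptoms or ECG changes, no recent surgery, and troponin that is at or past its peak at the first sample and then falls.

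| Route | Met? |
|---|---|
| Criterion 1, troponin rise | No: no rise was observed |
| Criterion 1, troponin fall | No: the peak is not post-surgical |
| Criterion 1, CK-MB | Only if both a rise and a fall are documented |
| Criterion 2 | Only with pathology |
| Criterion 3 | Only with new pathological Q waves |
| Unstable angina | No: biomarkers must be negative |
| Emergency revascularisation | Counts as MACE if within 1 month of new or progressive symptoms |
| Cardiovascular death | Counts as MACE |

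Coronary intervention is supporting feature d of criterion 1, but it does not replace the biomarker pattern. Emergency revascularisation can therefore restore MACE while the event stays uncounted as MI.

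Two comparison cases: the same falling pattern shortly after transplantation meets criterion 1, and so does a wait-listed patient whose rise was captured.

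**Step 2: events behind 80% power.** The protocol states no event count. With margin 1.25, true HR 1.00, two-sided 5% and equal allocation (assumed), Schoenfeld's formula gives

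d = 4 × (1.960 + 0.842)² / (ln 1.25)² = 631.

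**Step 3: events lost.** The protocol gives none of the shares needed, so all three are assumptions: MI as a share of MACE (40-60%), MIs first sampled at or after the peak (10-25%), and events on the waiting list (60-80%). No rescue by any other route is allowed.

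- Low: 631 × 0.40 × 0.10 × 0.60 = 15 (2.4%)
- Middle: 631 × 0.50 × 0.15 × 0.70 = 33 (5%)
- High: 631 × 0.60 × 0.25 × 0.80 = 76 (12%)

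**Step 4: power left.** Power = Φ(ln(1.25) × √d / 2 − 1.960).

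| Events | ln(1.25) × √d / 2 | Minus 1.960 | Power |
|---|---|---|---|
| 631 | 2.803 | 0.843 | 80% |
| 616 | 2.769 | 0.809 | 79% |
| 598 | 2.728 | 0.768 | 78% |
| 555 | 2.628 | 0.668 | 75% |

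Because Step 3 ignores CK-MB, pathology, Q waves, revascularisation and death, these losses are upper bounds for the shares assumed.

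**The case against.** The strongest reply is that the gap is narrow and cheap in power. Table 2 leaves five other routes open, and criterion 3 was evidently written with mistimed troponin in mind. The middle case costs two percentage points. By comparison, the accrual period, which section 10.2 does not give, moves power from about 81% (2-year accrual, 10% loss spread over follow-up) to about 73% (3-year accrual, flat 10% loss). Nor does section 10.2 say which MI definition underlies the 6% rate, so subtracting these events from the planned number is itself an assumption. All of this stands and limits the size of the point. It does not remove the point, since criterion 3 helps late presenters only if they have new Q waves.

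Three stronger readings are tempting, and the documents do not support them:

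- **That every such patient drops out of MACE.** Fatal, urgently revascularised and Q-wave events still count, as do those with pathology or a documented CK-MB rise and fall.
- **That the surgical condition also governs the rise, so that wait-list MIs lose the troponin route altogether.** The grammar does not exclude this, but the phrase attaches more naturally to the fall. Nothing in the protocol suggests that MI was meant to be confined to surgical patients. No power figure should be built on this reading; the ambiguity is one more reason to reword.
- **That the comparison is biased in a known direction.** If both arms lose true events in the same proportion, the hazard ratio is roughly unchanged. Bias needs the arms to differ in exposure to surgery and falling-only MIs to matter within that difference. The protocol quantifies neither.

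It may also be said that adjudicators would use common sense. Section 11.1 mentions an event adjudication committee, but the protocol contains no rule allowing it to depart from Table 2. Its working rules are not shown and may already deal with this.

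**Conclusion.** The point holds as a wording defect in a primary endpoint component. Followed literally, Table 2 misses a surviving, non-Q-wave MI outside surgery that is first sampled at or after the troponin peak, unless CK-MB or pathology supplies the evidence. Without emergency revascularisation within the month, the event is lost from MACE too. With it, MACE is restored but the MI secondary endpoint remains under-counted.

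The likely cost in power is modest: from 80% to about 79-75% if 2-12% of MACE were lost. That range rests entirely on assumed shares, on 631 events as the requirement, and on no rescue by other routes. The dependence of ascertainment on surgery is real in the text, but its effect on the hazard ratio has no known size or direction. Correction is worthwhile because the rule as stated misclassifies some true events and is easy to change.

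**What to change.** In Table 2, MI criterion 1, remove the condition that the peak be detected after surgery. The troponin limb would then accept *a typical rise and/or fall of troponin, at any time on the waiting list or after transplantation*. Keep the exclusion for a documented alternative cause and supporting features a to e. They protect specificity, which matters in a non-inferiority trial because non-specific events pull the hazard ratio towards 1.

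Use the same wording in the event adjudication rules. If any events have already been adjudicated, re-review those with a falling-only troponin, blinded to arm.

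The cost is a one-line amendment, matching adjudication text and a small amount of re-review. No additional patients are needed. Re-review can reach only cases where serial troponin values are available, and the protocol does not show that these are collected for every event.
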